Study: The Effects of OMT on the Expression of Immune Cell Biomarkers Study Protocol Document Date: October 31, 2018 NCT03250312

The Effects of Osteopathic Manipulation on the expression patterns of immune cell biomarkers

1. Specific Aims:

This proposal intends to study the effects of osteopathic manipulative treatment (OMT) on the biomarker expression patterns in human immune cells, by using the novel protein subcellular localization (PSL) microarray technology developed in [name] (PI) lab. The PSL microarray is the third generation of biochips (after DNA microarray, protein microarray) that can determine both the expression and subcellular localization protein profiling in high throughput screening format allowing for rapid identification of thousands of proteins. For the current study, we propose to use the PSL technology to determine the expression patterns of 60-400 cell surface proteins/biomarkers in human peripheral blood mononuclear cells (PBMC) of study participants with a history of low back pain, before and after OMT. We propose to identify and validate those proteins whose expression levels have been changed in most participants after OMT. From this study, we shall develop a platform to study the effects of different kinds of OMT techniques on participants with various types of pain conditions, and uncover the important immune cells that are affected by OMT techniques, therefore to uncover the molecular mechanisms of OMT.

Here are the specific aims for the current proposal:

Specific Aim 1: Determine the expression patterns of 60 surface biomarkers for human immune cells in PBMC of the participants, before and after OMT.

Specific Aim 2: Identify those specific proteins whose expression patterns have changed the greatest number of participants after OMT.

2. Research Strategy

2-1. Significance: Within the osteopathic profession most research on the effect of OMT on the immune system has involved lymphatic pump techniques. These techniques involve rhythmic compressions applied to the chest or abdomen, or through the lower extremities to maximize pressure gradients between the thorax and abdomen (page 632, 1). Studies performed in the 1920's and 30's found increases in serum leukocytes (2-3) and antibody titers (4) with splenic lymphatic pump techniques. Contemporary studies have detected changes in serum immune cell concentrations and inflammatory markers in response to lymphatic pump techniques. Mesina et al (5) measured blood cell counts following pectoral traction and splenic pump techniques and found significantly increased basophil counts in the 15-60 minute period post-treatment. However, there was individual variability with one subject demonstrating a significant increase persisting 4 hours post-treatment. Noll et al (6) found a decrease in serum platelet counts after participating nursing home residents received a single 6 minute OMT treatment consisting of lymphatic and myofascial techniques. Walkowski et al (7) found increases in serum cytokines, including IL-6, with a single 7-minute lymphatic treatment consisting of thoracic, splenic, and hepatic pump techniques. Licciardone et al (8) found several cytokines that were significantly associated with low back pain. Of these inflammatory markers, tumor necrosis factor concentrations significantly decreased after 12 weeks with 6 OMT sessions. These changes in serum immunologic factors

may be due to the OMT techniques' effect on the central lymphatic system. Lymphatic pump techniques have been shown to transiently increase central lymphatic flow, lymph leukocyte concentrations, and IL-6 concentrations (9-13).

Changes in lymphatic markers have been seen with other types of manual techniques. Soft tissue massage has been shown to significantly increase thymic and splenic T cell number in mice (14), increase serum natural killer cell and lymphocyte numbers in women with early stage breast cancer (15), and increase natural killer cell cytotoxicity in stable preterm infants (16). Serum from participants receiving spinal manipulation (HVLA) has been shown to significantly increase *in-vitro* immunoglobulin G and IL-2 synthesis in peripheral blood mononuclear cells (17-18). Spinal manipulation has also been shown to modify serum IL-6 levels (19) and decrease lymphocyte activation (20). The proposed study will expand upon the biomarker evidence base by investigating the effects of OMT on the biomarker expression patterns in serum immune cells using the PSL (protein subcellular localization) microarray technology.

The PSL (protein subcellular localization) microarray technology is the novel technology developed in [name] lab. It provides a unique approach to simultaneously determine subcellular localization and expression profiles of potentially thousands of proteins from one experiment. The technology has been already been used to identify the differences in protein expression between normal and cancer breast cell lines (21-23). The technology has also identified proteins with unique subcellular localization patterns between normal and cancer cells with breast origin and prostate origin (21-23).

2-2. Innovation: We propose to study the effects of OMT on serum immune cells using a system biology approach through the use of novel PSL microarray technology. No studies have yet investigated the effects of OMT using this technology, which may be able to detect changes in biomarker expression on immune cells even in the absence of cell concentration changes. We propose to use 40 participants for the experiments, 20 in the OMT group, and 20 in the control group. This number of participants should give us adequate statistical power to detect the difference in biomarker expression change. In addition, this proposal could provide a platform for future studies investigating the effects of different OMT techniques, and therefore to understand the molecular mechanism for OMT.

2-3. Preliminary data:

2-3a. Summary of the PSL microarray technology and its application on biomarker identification (Ref). The PSL microarray technology, also known as DAMA staining technology, is a novel technology that has combined the power of immunohistochemical staining and the parallel analysis of antibody microarrays (2123). It is equivalent to carry out 1000 immunostaining experiments from single immunostaining experiment. To our knowledge, this is the unique technology that can determine both the subcellular localization and expression profiles of thousands of proteins in high-throughput format.

[name]

Instead of capturing ligands on the array support like DNA microarray, PSL microarrays deliver multiple antibodies to their antigens in a position-addressable manner (Fig. 1). In this method, cells grown to the desired states on the cover slip, are fixed and permeabilized with standard methods (step 1). An array of antibodies on a membrane is then placed on the top of the cell with the antibodies facing the cells and incubated for an hour. During the incubation, antibodies dissociate from the array membrane and bind to their respective antigens in the cells without significant lateral diffusion (step 2). Afterward, the array membrane is removed, leaving the bound antibodies attached to the cellular antigens *in situ* (step 3). Enzyme-labeled secondary antibodies are then used to detect the bound primary antibodies on the cells (step 4). This way, the expression levels of multiple antigens can be determined simultaneously.

When fluorophore-conjugated secondary antibodies, instead of enzyme-labeled secondary antibodies, are used to detect the bound antibodies (step 4, Fig. 1), both the expression level and cellular localizations of multiple antigens can be determined using the fluorescent or confocal microscopes.

[figure not shown]

Fig. 1. Schematic representation of the PSL microarray technology

Identification of potential biomarkers for breast cancer by using the PSL microarray technology. (21) [name] lab has developed the PSL microarray technique and demonstrated its application on identifying the differentially expressed proteins between normal and cancer breast cell lines (4). For this purpose, protein expression profiles of ten different cell lines from human mammary glands were obtained using the PSL microarray technology and subjected to intensity integration and data analysis. Ten proteins were identified by DAMAPEP, (DAMA protein expression profiling, a software developed at his lab to retrieve, normalize, scale and analyze the intensity data), to have differential expression levels in cancer cells versus normal cells. Five proteins, RAIDD, Rb p107, Rb p130, SRF and Tyk2, were identified to have higher expression levels in cancer cells, and were confirmed by western blotting analysis (21).

Identification of potential biomarkers with different subcellular localizations for breast cancer and prostate cancer, by using PSL microarray technology (22-23). [name] lab has developed the PSL microarray technology that provides a new approach to the global analysis of protein subcellular localization (SCL) profiling in fixed cells. His lab has developed and optimized this technology, generated ChipView, a program for management and analysis of molecular image database, and utilized the technique to identify

proteins with unique SCL in breast cancer cell lines. The subcellular profile images of 360 proteins in a normal breast cells are shown in Fig 2a, and the subcellular localization profiles of the 360 proteins in two benign and seven carcinoma cells are shown in Fig 2b. From data analysis, a protein, Cyclin B1, was identified and validated with different SCLs between normal and cancer cell lines (22). Similar research has been carried out in prostate cancer and normal cell lines (23).

[figure not shown]

Fig 2. (A, left) Summary of representative molecular images of 360 proteins in one normal breast cell, as determined by the DAMA staining technology (22). Each image represents the image of the corresponding protein in the tested sample. Images shown were taken with 63x objective lens. (B, right) Subcellular localization (SCL) profiles of 360 proteins in two benign and seven carcinoma derived cells, presented with a custom-defined color code scheme. Red indicates a protein is localized to the nuclei, green indicates a protein is localized to the cytoplasm, yellow indicates a protein is localized both to nuclei and in cytoplasm, and black represents an uncertain SCL for the protein. Each column represents the SCL codes of the proteins in the same cell line, and each row represents the SCL codes of the same protein in different cell line samples.

2-3b. Summary of the funded study on "identify novel biomarkers for sDILI (severe Drug Induced Liver Injury) by using novel PSL microarray technology (was called DAMA staining technology). This grant proposal was funded by the Warner / Fermaturo research grant. [name] lab has studied the effects of different compounds on the expression profiles of 23 different Cytochrome P450s in HepG2 cells.

His lab has obtained 9 different compounds, 3 sDILI compounds (Ketoconazole, Troglitazone, Flutamide) and 6 non-sDILI compounds (Erythromycin freebase, Erythromycin estolate, SDS, Budesonide, Nicardipine, Olmesartan). The expression profiles of 23 different cytochrome P450s (CYPs) in the HepG2 cells treated with those compounds and controls are obtained and summarized in Fig 3. Unfortunately, no differentially expression changes for any P450 subtype proteins were observed between cells treated with different concentration (40 M and 80 M) of sDILI compounds and non-sDILI compounds.

Treatment of flutamide has been reported to increase the expression of liver cytochrome P450 1A2 (24). Therefore, his lab has determined the expression profiles of 23 different cytochrome P450s in the HepG2 cells treated with different concentration of Flutamide, (0 - 250 M) (Fig 4). No increase of cytochrome P451A2 was observed either.

[figure not shown]

Fig. 3. The expression profiles of 23 CYPs in HepG2 cells treated with different compounds and control (#0). The expression profiles were determined in triplets.

[figure not shown]

OMT intervention: The OMT treatment will begin with a brief physical examination to identify somatic dysfunction that the treating physician judges to be relevant to the individual participant's low back pain. OMT will be performed to improve the somatic dysfunctions that the treating physicians finds most relevant. The types of OMT techniques used will include muscle energy, articular, or high velocity-low amplitude (HVLA) as indicated by the physical findings and will be at the discretion of the treating physician. Additional techniques such as still, counter strain, facilitated positional release, balanced ligamentous tension, and cranial techniques may also be used at the discretion of the treating physician. The treatment will conclude with 2 minutes of pedal lymphatic pumping technique. The total treatment time will not to exceed 20 minutes. To encourage participation in the proposed study, participants who are assigned to the control group will have an opportunity to receive OMT after the second blood draw.

Control protocol: The control group will wait in another room for approximately 30 minutes.

PBMC cell isolation. PBMC cells will be isolated and prepared according to the company protocol which is summarized as below. Venous blood will be collected via venipuncture into the Vacutainer CPT tube (BD Biosciences). CPT tubes will be centrifuged at 1800 x g for 20 minutes at room temperature. After centrifugation, CPT tubes will be brought to a biological safety cabinet and carefully opened. The PBMC cells, which are in the layer just under the plasma (Figure 5), will be transferred to a 15 ml conical tube. The conical tubes will be centrifuged at 250 x g for seven minutes at room temperature. The PBMC cells will be re-suspend at 5 x 10^6 viable lymphocytes per ml in PBS buffer.

[name]

Coverslip preparation. 100⁴ of the suspended PBMC cells will be added to a poly-lysine coated coverslip (22 mm x 22 mm), and dried for 10-20 minutes at room temperature. The cells attached to the coverslips will be washed three times in PBS, and fixed with 4% paraformaldehyde in PBS. The detail protocol would be modified and optimized in the experiments.

Antibody selection and microarray preparation. The goal of this project is to purchase ~60 antibodies, which are the surface biomarkers for different human immune cells. We shall determine the expression patterns of the 60 proteins in the PBMC cells from the participants, before and after the OMT treatment by using the PSL microarray. The proteins with differentially expressed level after the OMT treatment will be identified from data mining and statistical analysis.

We plan to first purchase 30 antibodies, which are the biomarkers for different human lymphocytes. The selected antibodies and their major expression in different lymphocytes are summarized in Table 1. The PSL microarrays containing those antibodies will be made according the design in figure 6 by using the purchased antibodies and the nanoplotter at ATSU, and will be used for the proposed research. Most of the 30 proteins shown in Table 1 are expressed in 1-2 kinds of different lymphocyte cells. An increase or decrease in expression of those proteins could be related to the increase or decrease of the specific types of lymphocytes, which could provide potential mechanism for OMT on immune system activity.

The second set of 30 antibodies will be selected from the \sim 150 surface proteins summarized in the Appendix (with their expression patterns in human immune cells) and purchased later pending the findings from the analysis of the first 30 antibodies. The samples will be saved and stored in liquid nitrogen and retested for the second set of 30 antibodies.

The long-term plan. The long-term plan of the proposal is develop a research methodology for study the effect of OMT on immune system activity. The goal of the current proposal is to generate preliminary data, so that we could apply for the NIH grant to determine the expression patterns of 150-200 cell surface biomarkers for human immune cells in the PBMC cells of the participants, before and after OMT. For this purpose, a grant application based on the preliminary data generated from the current proposal will be submitted to NIH or AOA. Additional antibodies, as those listed in the Appendix, will be purchased if funded. The microarray containing 150-200 antibodies will be made similar to those used in the publication (23), and used for the longterm research.

Table 1. Summary of Antibodies used for the research and their expression in immune cells

B Cells Markers	Myeloid and mast	IK Sell	s	T Cells

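### With every sample set to a fixed lymphocyte concentration, the After/Before ratio is relative to lymphocytes, so a marker change cannot safely be read as a change in cell number

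*Protocol*

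**What the plan says.** Protocol 2-4 Approach, PBMC cell isolation, fixes the suspension: "The PBMC cells will be re-suspend at 5 x 10^6 viable lymphocytes per ml in PBS buffer". Coverslip preparation then gives one amount of suspension for every coverslip (its unit is not readable in the text at hand). Before and After coverslips thus nominally carry the same number of lymphocytes.

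Data Extraction and data analysis takes the After/Before intensity ratio of each marker and compares the arms by two-sample t-test. The DAMAPEP software normalises and scales intensities. The comparison with control is expected to isolate the changes caused by OMT.

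Two readings of a marker change are offered:
- Antibody selection and microarray preparation: "An increase or decrease in expression of those proteins could be related to the increase or decrease of the specific types of lymphocytes", put forward as a possible mechanism.
- 2-2 Innovation: the technology "may be able to detect changes in biomarker expression on immune cells even in the absence of cell concentration changes".

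Section 1 also hopes to "uncover the important immune cells that are affected by OMT techniques", and the background in 2-1 notes: "Contemporary studies have detected changes in serum immune cell concentrations and inflammatory markers in response to lymphatic pump techniques". The protocol does not say that the cell count from the re-suspension step is kept as data or used in the analysis.

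**The concern.** The cell-number reading needs a signal that moves with the number of cells in blood. Loading to a fixed lymphocyte concentration takes that information out before staining. If OMT changes the lymphocyte total, the After sample is diluted or concentrated by exactly that change. Lymphocyte markers then look stable, and markers of cells that did not change appear to move the other way.

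Two errors could follow: a real rise in lymphocytes goes unseen, and an unaffected cell type is reported as reduced by OMT. Later analysis cannot repair either if the count was not written down at the bench.

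**Working it through.** **Inputs from the protocol.** Suspension fixed at 5 x 10^6 viable lymphocytes per ml. Endpoint After/Before ratio, OMT against control. SDs 0.34 (control) and 0.32 (intervention), target difference 0.5, 11 per group by calculation and 20 per group planned. Table 1 lists CD11b, CD11c, CD14 and CD163 under monocytes.

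**Assumed, because the protocol gives no figures.** Size of any cell shift, subset shares, and spot signal proportional to the cells present.

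**1. The plan's own figure.** Standard error with 11 per group = sqrt((0.34² + 0.32²)/11) = sqrt(0.218/11) = 0.141. The two-sided Welch t-test then has power 0.922 for a difference of 0.5, against 0.92 stated. The sample-size arithmetic is not in question. With 20 per group, power is 0.997.

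**2. General lymphocyte rise.** Let lymphocytes per ml of blood change by a factor f and monocytes by h. After fixed-lymphocyte loading:
- lymphocyte marker ratio = f/f = 1
- monocyte-only marker ratio = h/f, which is 1/f when monocytes are unchanged

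| f (assumed) | Lymphocyte markers | Unchanged monocyte markers |
|---|---|---|
| 1.1 | 1.00 | 0.91 |
| 1.25 | 1.00 | 0.80 |
| 1.3 | 1.00 | 0.77 |
| 1.5 | 1.00 | 0.67 |
| 2 | 1.00 | 0.50 |

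**3. Rise in one lymphocyte subset.** Let a subset with share s of lymphocytes rise by a factor g. The lymphocyte total rises by D = 1 + s(g − 1). The subset reads g/D and all other cells read 1/D.

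| s | g | Subset reads | Other cells read |
|---|---|---|---|
| 0.10 | 1.5 | 1.43 | 0.95 |
| 0.20 | 1.5 | 1.36 | 0.91 |
| 0.70 | 1.5 | 1.11 | 0.74 |

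An NK share rising from 10% to 15% of lymphocytes means 10x/(90 + 10x) = 0.15, so x = 1.59. NK markers read 1.50 and other cells 85/90 = 0.94. A 1.5-fold change in expression per cell also reads 1.50, so the ratio alone cannot separate these two causes.

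**4. What the t-test would see** (20 per group, protocol SDs, two-sided 0.05 for one marker, control ratio 1):
- General rise f = 1.5: power for lymphocyte markers is 0.05, because no difference is left; it would be 0.997 if the rise were not normalised out. The chance of declaring the false monocyte fall is 0.875. With the control mean of 1.32 from Table 2, the false difference is 1.32 − 1.32/1.5 = 0.44 and that chance is 0.984.
- 1.5-fold rise in a 70% subset: power 0.18 for the subset itself, 0.68 for the false fall in other cells.
- 1.5-fold rise in a 10% to 20% subset: power 0.98 to 0.92.
- 1.5-fold rise in expression per cell: power 0.997.

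**5. Does the control arm help?** A shift caused by OMT gives f ≠ 1 in the OMT arm only. The between-arm difference keeps the artefact in full. Scaling of intensities brings in no cell count.

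**6. Does a count-scaled ratio help?** Multiply by the After/Before lymphocyte count per ml of blood. In step 2, lymphocytes give 1 × f = f and unchanged monocytes give (1/f) × f = 1. In step 3, the subset gives (g/D) × D = g and other cells (1/D) × D = 1. All are the true cell-number changes, apart from recovery error.

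**The case against.** Equal lymphocyte loading is a natural choice for a question about expression. Both Specific Aims concern expression patterns, the cell-number reading is hedged and refers to specific cell types, and relative shifts between types largely survive. Any bulk signal on a mixed cell layer confuses number with expression, so loading by blood volume would not remove that ambiguity. The shift sizes are assumed, and to match the 0.5 effect through the monocyte artefact lymphocytes would have to double around a single session. Drying and washing make the real loading only nominal, and the protocol leaves room for change: "The detail protocol would be modified and optimized in the experiments".

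Most of this stands, and it limits the point. A reader might infer that the trial cannot say which immune cells OMT affects. The documents do not support that: steps 3 and 4 show that small-subset shifts and per-cell changes remain visible. A reader might also infer that lymphocyte mobilisation is the effect the protocol most expects. It predicts no general rise in blood lymphocytes; 2-1 is background on several cell types and mediators.

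The false monocyte fall does require lymphocytes to rise more than monocytes. If both rise equally, h/f = 1 and there is no false fall, but the rise is then hidden in every marker. The optimisation clause names no change to the count step. Hedged or not, the cell-number reading is the one that this loading weakens.

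**Conclusion.** The point holds in a limited form. The ratio measures composition and expression relative to lymphocytes, not blood cell numbers. A general lymphocyte rise is fully masked in lymphocyte markers, a rise in a dominant subset is largely masked, and unchanged cells then show a false fall: 1/f, or 0.77 at f = 1.3 and 0.67 at f = 1.5. The control arm leaves this in place.

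The expression aim survives. What fails is the inference from a marker change to a change in cell number when only the ratio is available. The sizes rest on assumed shifts, proportional signal and markers specific to one cell type. The columns of Table 1 are partly unreadable in the text at hand, and a marker shared between monocytes and lymphocytes would read between 1/f and 1.

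**What to change.** 1. For both draws, record the viable lymphocyte count that the re-suspension step already requires, with the blood volume and the re-suspension volume.
2. Compare the After/Before lymphocyte count per ml of blood between the arms.
3. Report each marker ratio twice: as measured, and multiplied by the After/Before count ratio.
4. Reword the interpretation under Antibody selection and microarray preparation: the unscaled ratio is relative to lymphocytes and does not separate cell number from expression per cell. The scaled ratio corrects the cell-number scale, but it does not separate the two either.

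Rescaling subset markers to CD3 is not recommended, because Table 1 appears to mark CD45RA, CD45RO, CD25 and CD8 on cells other than T cells.

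The cost is a few recorded values per sample, one multiplication in the analysis and a reworded paragraph; no new assay is needed. The downside is that cell recovery varies from tube to tube and adds noise to the scaled ratio. It should therefore stand beside the unscaled ratio and not replace it.
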